	
participant/parent/guardian about the importance of taking the study drug as prescribed.
 
 
• For ferrous sulfate drops and elixir:           
 
○ If the participant took less than the volume expected, document the reason(s) for dose reduction and counsel the participant/parent/guardian about the importance of taking the study drug as prescribed.
 
 
 
 
New Wording:
 
Group A:
 
 
• Blood samples for PK immediately (within 5 minutes) post-dose and 60 minutes post dose.
 
• Post-administration, obtain sitting heart rate and blood pressure immediately (within 5 minutes) after and 30 minutes after FCM administration.
 
 
Group B
 
 
• Oral ferrous sulfate dispensing:           
 
○ If the participant took less than the number of tablets expected, document the reason(s) for missed doses and counsel the participant/parent/guardian about the importance of taking the study drug as prescribed.
 
 
 
• For ferrous sulfate drops and elixir:           
 
○ If the participant took less than the volume expected, document the reason(s) for missed doses and counsel the participant/parent/guardian about the importance of taking the study drug as prescribed.
 
 
 
	

6.3.6 PHARMACOKINETIC SAMPLING
	
Original Wording:
 
Blood samples will be collected for PK assessment pre-dose, immediately post-dose, and 60 minutes post-dose for participants receiving FCM on Days
	
To clarify the time for blood sampling.

	
0 and 7. Blood samples should be taken at approximately the same time of day on Day 7 as Day 0.
 
New Wording:
 
Blood samples will be collected for PK assessment pre-dose, immediately (within 5 minutes) post-dose, and 60 minutes post-dose for participants receiving FCM on Days 0 and 7. Blood samples should be taken at approximately the same time of day (within 1 hour) on Day 7 as Day 0.
	
7.1 ADVERSE EVENTS	
Original Wording:
 
To quantify the severity of adverse events, the National Cancer Institute (NCI)-Common Terminology Criteria for Adverse Events (CTCAE), Version 4 should be used to grade all events. These criteria are provided in the procedure manual.
 
New Wording:
 
To quantify the severity of adverse events, the National Cancer Institute (NCI)-Common Terminology Criteria for Adverse Events (CTCAE), Version 5 or higher should be used to grade all events. These criteria are provided in the procedure manual.
	To make sure the latest version of the NCI CTCAE is used
7.3 SERIOUS ADVERSE EVENTS	
Original Wording:
 
Email: [contact]
 
New Wording:
 
Email: [contact]
	To reflect the change in the e-mail for Pharmacovigilance
8.4.1 PRIMARY ENDPOINTS Subgroup analyses	
Original Wording:
 
The change in hemoglobin from baseline to day 35 will be summarized separately for the following subgroups:
 
 
• Cause of IDA: IBD, not IBD
 
• Baseline hemoglobin : <10, ≥10 g/dL
 
	Since children with chronic kidney disease on hemodialysis are allowed to participate in the study, they

	
 
• Age: 1 to <12, ≥12 to 17 years
 
 
New Wording:
 
The change in hemoglobin from baseline to day 35 will be summarized separately for the following subgroups:
 
 
• Cause of IDA: IBD, not IBD
 
• CKD, not CKD
 
• Baseline hemoglobin : <10, ≥10 g/dL
 
• Age: 1 to <12, ≥12 to 17 years
 
	
were included in the subgroup analyses


8.4.2 SECONDARY ENDPOINTS
	
Original Wording:
 
Secondary efficacy endpoints include:
 
 
• Change in ferritin from baseline to Day 35
 
• Change in TSAT from baseline to Day 35
 
• Changes from baseline to in hemoglobin, ferritin, TSAT, and reticulocyte hemoglobin content.
 
• Pharmacokinetic assessments, including <math>C_{max}</math>, <math>T_{max}</math>, <math>AUC_{0-time\ last\ measured\ concentration}</math>, <math>AUC_{0-infinity}</math>, <math>T_{1/2}</math>, <math>MRT</math>, <math>Cl</math>, <math>V_D</math>, <math>V_{Dc}</math>, <math>V_{Dss}</math>, and <math>V_{Darea}</math>.
 
 
New Wording:
 
Secondary efficacy endpoints include:
 
 
• Change in ferritin from baseline to Day 35
 
• Change in TSAT from baseline to Day 35
 
• Changes from baseline to in hemoglobin, ferritin, TSAT, and reticulocyte hemoglobin content.
 
• Pharmacokinetic assessments, including <math>C_{max}</math>, <math>T_{max}</math>, <math>AUC_{0-time\ last\ measured\ concentration}</math>, <math>AUC_{0-infinity}</math>, <math>T_{1/2}</math>, <math>MRT</math>, <math>Cl</math>, <math>V_D</math>, <math>V_{Dc}</math>,
 
	
To clarify pharmacokinetic assessment

	
<math>V_{Dss}</math>, and <math>V_{Darea}</math>. These assessments will be based on a population pharmacokinetic analysis using data from this study and 1VIT13036.
	

8.5.4 CLINICAL LABORATORY FINDINGS
	
Original Wording:        Clinical laboratory variables will be presented in two ways. First, the mean change from baseline to each scheduled visit will be summarized. Second, the number and percent of participants with treatment-emergent PCS laboratory values will be tabulated. Treatment-emergent PCS laboratory tests are those in which the baseline value is normal and post-baseline value is abnormal (i.e., meets Grade III or Grade IV toxicity criteria from the NCI-CTC). Baseline will be defined as the last value obtained before randomization.
 
New Wording:        Clinical laboratory variables will be presented in two ways. First, the mean change from baseline to each scheduled visit will be summarized. Second, the number and percent of participants with treatment-emergent PCS laboratory values will be tabulated. Treatment-emergent PCS laboratory tests are those in which the baseline value is normal and post-baseline value is abnormal (i.e., meets Grade III or Grade IV toxicity criteria from the NCI-CTC Version 5 or higher). Baseline will be defined as the last value obtained before randomization.
	
To update the version of NCI-CTC to be used.

### ADMINISTRATIVE CHANGE 1

Affected Section(s)	Summary of Revisions Made	Rationale

HEADER
	
The heading was changed to reflect the current protocol version number and date of version.
 
Original Wording:
 
American Regent, Inc.                      Protocol No.: 1VIT17044 CONFIDENTIAL                                      Amendment 2 Date: 13 March 2019
 
New Wording:
 
American Regent, Inc.                      Protocol No.: 1VIT17044 CONFIDENTIAL                                      Administrative Change 1 Date: 26 September 2019
	
To reflect the updated version of the protocol.

TITLE PAGE
	
Protocol Date was changed.
 
Original Wording:
 
Protocol Date: 20 April 2017 Amendment I Protocol Date: 14 September 2017 Amendment 2 Protocol Date: 13 March 2019
 
New Wording:
 
Protocol Date: 20 April 2017 Amendment 1 Protocol Date: 14 September 2017 Amendment 2 Protocol Date: 13 March 2019 Administrative Change 1 Date: 26 September 2019
	
To reflect the date of the current protocol version.


SIGNATURES OF AGREEMENT FOR PROTOCOL
	
Removal of: [name], DPM, Medical, Director, Head of Pharmacovigilance [name], Director of Regulatory Affairs [name], Head of Quantitative Sciences
	
An Administrative Change does not need all functions to approve.

Section 4.2.1 INCLUSION CRITERIA	
Original Wording: 4. Documented history of an inadequate response to any oral iron therapy for at least 8 weeks (56 days) prior to screening.
 
New Wording: 4. Documented history of an inadequate response to any oral iron therapy for at least 8 weeks (56 days) prior to randomization.
	To revert back to the inclusion criteria # 4 sentence in the original protocol and Amendment 1.

**LIST OF ABBREVIATIONS AND DEFINITIONS**

AST	Aspartate Aminotransferase Test
ALT	Alanine Transaminase Test
ATC	Anatomical Therapeutic Chemical
ANCOVA	Analysis of Covariance
AUC 0–infinity	Extrapolated Area Under the Serum Concentration- time Curve from Time Zero to Infinity
AUC 0–time last measured concentration	Area Under the Serum Concentration-time Curve from Time Zero to the Last Sampling Time with a Quantifiable Concentration
BP	Blood Pressure
BUN	Blood Urea Nitrogen
eCRF	Electronic Case Report Form
C max	Maximum Serum Concentration
CHr	Reticulocyte Hemoglobin Content
Cl	Apparent Serum Clearance
CI	Confidence Interval
DSMB	Data and Safety Monitoring Board
ESA	Erythropoietin Stimulating Agent
FCM	Ferric Carboxymaltose
GGT	Gamma-Glutamyl Transferase
Hct	Hematocrit Test
Hgb	Hemoglobin
IDA	Iron-deficiency Anemia
IBD	Inflammatory Bowel Disease
IRT	Interactive Response Technology
IV	Intravenous
LDH	Lactate Dehydrogenase
MCH	Mean Cell Hemoglobin
MCHC	Mean Corpuscular Hemoglobin Concentration
MCV	Mean Corpuscular Volume
MedDRA	Medical Dictionary for Regulatory Activities
MRT	Mean Residence Time
mg	Milligrams
PCS	Potentially Clinically Significant
PE	Physical Examination
PT	Preferred Term
RBC	Red Blood Cells
RDW	Red Cell Distribution Width
SAE	Serious Adverse Event
SAP	Statistical Analysis Plan
SOC	System Organ Class
SD	Standard Deviation

$T_{\max}$	Time at Which $C_{\max}$ Occurs
$T_{1/2}$	Half-life
TEAE	Treatment Emergent Adverse Event
TIBC	Total Iron Binding Capacity
TSAT	% Transferrin Saturation
$V_D$	Apparent Volume of Distribution
$V_{Dc}$	Apparent Volume of Distribution Includes the Initial Volume of Distribution Following the Injection
$V_{Dss}$	Volume of Distribution at the Steady State
$V_{Darea}$	Volume of Distribution at the Final Elimination
WBC	White Blood Cells
WHO	World Health Organization

## 1. INTRODUCTION

The purpose of this statistical analysis plan (SAP) is to describe the procedures and the statistical methods that will be used to analyze and report results for Protocol 1VIT17044 (Administrative Change 1 Protocol Date: 26 SEP 2019). This SAP pertains to clinical safety and efficacy analysis and should be read in conjunction with the study protocol and electronic case report forms (eCRFs). Pharmacokinetic analyses are out of scope for this SAP.

### 1.1 STUDY OBJECTIVES

#### 1.1.1 Primary Objective(s)

The primary objective of this study is to demonstrate the efficacy and safety of intravenous (IV) ferric carboxymaltose (FCM), compared to oral iron, in pediatric participants who have iron deficiency anemia (IDA).

### 1.2 STUDY ENDPOINTS

#### 1.2.1 Primary Efficacy Endpoint

Change in hemoglobin from baseline to Day 35.

#### 1.2.2 Secondary Efficacy Endpoint(s)

- Change in ferritin from baseline to Day 35
- Change in transferrin saturation (TSAT) from baseline to Day 35
- Changes from baseline in hemoglobin, ferritin, TSAT, and reticulocyte hemoglobin content (CHr) throughout the study.
- Pharmacokinetic assessments, including  $C_{max}$ ,  $T_{max}$ ,  $T_{1/2}$ , MRT, Cl,  $V_D$ ,  $V_{DC}$ ,  $V_{DSS}$ ,  $V_{Darea}$ ,  $AUC_{0-\infty}$  and  $AUC_{0-\text{time last measured concentration}}$ . These assessments will be based on a population pharmacokinetic analysis using data from this study and the 1VIT13036 study.

The analysis of PK assessments is not addressed in this SAP.

#### 1.2.3 Safety Endpoints

Safety endpoints include:

- Extent of exposure
- Adverse events
- Laboratory assessments
- Vital signs

### 1.3 SUMMARY OF THE STUDY DESIGN

#### 1.3.1 General Study Design and Plan

This is a Phase III, multicenter, multinational, randomized, active-controlled study that compares the efficacy and safety of FCM to oral iron in pediatric participants with IDA and a documented history of an inadequate response to oral iron therapy at least 8 weeks (56 days) prior to screening.

FCM injection is a stable, non-dextran, Type I polynuclear iron (III) -hydroxide carbohydrate complex developed as an intravenous (IV) iron replacement therapy for the treatment of IDA. The duration of this study is approximately 6 weeks and the number of sites is approximately 30. Participants who satisfy the inclusion requirements and no exclusion criteria will be eligible to participate in this study and enter into a screening phase to confirm eligibility. All eligible participants will be randomized in a 1:1 ratio to receive either FCM at 15 mg/kg to a maximum single dose of 750 mg on Days 0 and 7 for a maximum total dose of 1500 mg in Group A or oral iron (oral solution drops, elixir or oral tablets) twice daily for 28 days in Group B. Randomization will be stratified by baseline hemoglobin (<10,  $\geq$ 10 g/dL) and age (1 to <12 and  $\geq$ 12 to 17 years). The oral ferrous sulfate formulation received will be based on the participant's age, such that infants and children (1 to <4 years of age) will receive ferrous sulfate drops, children ( $\geq$ 4 to <12 years of age) will have the option to receive ferrous sulfate elixir or ferrous sulfate tablets, and adolescents ( $\geq$ 12 to 17 years of age) will receive ferrous sulfate tablets. If the participants experience adverse clinical symptoms due to the oral iron during the treatment phase, the weight-based dose of ferrous sulfate will be reduced from 6 mg/kg to 3 mg/kg. As for the participants who receive tablets, the dose will be reduced from one tablet taken twice daily to one tablet per day.

Once randomized, all participants will return for efficacy and safety evaluations, including adverse events and laboratory assessments, on Days 7, 14, 28, and 35. Additional pharmacokinetic sampling and analyses will be performed for participants receiving FCM on Days 0 and 7.

The Schedule of Events is presented by Table 1.

Table 1 Schedule of Events

Visit Day	Screening (Day -7 + 1)	Day 0	Day 7	Day 14	Day 28	DAY 35
Informed Consent / Assent	X					
Medical History	X					
Physical Exam		X				X
Inclusion/Exclusion Criteria	X	X				
IRT	X	X				X
Vital Signs	X	X	X	X	X	X
Weight	X	X				
Height	X					
Temperature		X	X			
Hematology, Chemistry and Iron Indices 	X	X	X	X	X	X
Serum Pregnancy Test	X					X
Concomitant Medications	X	X	X	X	X	X
IBD Treatment / ESA Stability (if applicable)	X	X	X	X	X	X
Adverse Event Assessment		X	X	X	X	X
Randomization		X				
Injectafer ® Dosing		X	X			
Pharmacokinetic Sampling 		X	X			
Oral Iron Dosing		X	X	X	X	
Oral Iron Dispensing		X	X	X		
Oral Iron Compliance Assessment			X	X	X	

For a full description of central laboratory assessments, refer to Protocol Section 6.4.

Blood samples for pharmacokinetic analysis will be collected pre-dose, immediately (within 5 minutes) post-dose, and 60 minutes post-dose for participants receiving FCM. For a full description of the pharmacokinetic parameters, refer to Protocol section 6.3.6.

### 1.3.2 Stratification/Randomization

On Day 0, participants who meet the inclusion/exclusion criteria will be randomized via IRT system in a 1:1 ratio to receive either FCM in Group A or oral iron (oral solution drops, elixir or oral tablets) in Group B. Randomization will be stratified by baseline hemoglobin (<10, ≥10 g/dL) and age (1 to <12 and ≥12 to 17 years).

### 1.3.3 Blinding

The randomization schedule is generated by an independent randomization statistician. Although the study is open-label, other than designated randomization personnel, the study statisticians and the ARI statistician are blinded to study drug assignment prior to database lock.

### 1.3.4 Sample Size and Statistical Power Considerations

A total of 60 participants (30 per treatment group) are required to detect an expected difference in hemoglobin of 1.0 g/dL (common standard deviation = 1.16 g/dL) at two-sided  $\alpha=0.05$  with 90% power. Assuming attrition of subjects not being evaluable for efficacy analysis, approximately 72 participants will be randomized.

## 2. STATISTICAL METHODS

### 2.1 GENERAL CONSIDERATIONS

Analysis datasets will be produced according to CDISC standards. All study-collected data will be summarized in tables or graphs. Listing will be produced when appropriate and all ICH-required listings will be produced.

Continuous variables will be summarized by number of observations (n), mean, standard deviation (SD), median, quartiles (Q1 and Q3), minimum (min), and maximum (max) values. Other descriptive statistics (e.g., coefficient of variation) may be reported when appropriate. Analysis of categorical variables will include frequency counts and percentages. Unknown and missing data may be presented as a separate category and the denominator will include unknown or missing values as appropriate.

If applicable, hypothesis testing will be carried out at the two-sided  $\alpha=0.05$  level unless otherwise specified; 2-sided 95% confidence intervals (CIs) will be presented, where specified.

#### 2.1.1 Reporting Precision

Summary statistics will be presented to the following degree of precision, unless otherwise specified:

Statistics	Degree of Precision
------------	---------------------

Mean, Geometric mean, Median, Quartiles, Confidence limit boundaries	One decimal place more than the raw data.
Standard deviation, Standard error	Two decimal places more than the raw data.
Minimum, Maximum	The same as the raw data.
p-value	Rounded to 4 decimal places and therefore presented as 0. xxxx; p-values smaller than 0.0001 as '<0.0001'; p-values greater than 0.9999 as '>0.9999'.
Percentage	One decimal place. A percentage of 100% will be reported as 100%. Percentages of zero will be reported as 0.

For weight and height, one decimal place will be used for summary statistics. Fractional numeric values will be presented with a zero to the left of the decimal point (for example, 0.12 – 0.30).

## 2.2 DEFINITIONS OF ANALYSIS POPULATIONS (ANALYSIS SETS)

### 2.2.1 Intent-to-Treat Population

The Intent-to-Treat (ITT) population will comprise all randomized participants. Participants will be evaluated according to the treatment to which they were randomized. Any participant who receives a treatment randomization number will be considered to have been randomized. Unless otherwise stated, disposition and baseline data will be summarized in ITT population. The primary population for assessing efficacy will be the ITT population.

### 2.2.2 Modified Intent-to-Treat Population

The modified Intent-to-Treat (mITT) population will comprise all participants in the ITT population who receive at least one dose of study drug, have a baseline hemoglobin measurement, and at least one corresponding post-baseline measurement. Participants will be evaluated according to the treatment to which they were randomized. The mITT population may be used for *post hoc* sensitivity analyses.

### 2.2.3 Safety Population

The safety population will consist of all participants in the ITT population who received at least one dose of study drug. Participants will be evaluated according to treatment received. This population will be used for assessing safety.

## 2.3 DEFINITIONS AND CONVENTIONS FOR DATA HANDLING

### 2.3.1 Baseline Definition

For evaluations collected at multiple time points, the baseline will be defined as the last value obtained before randomization.

### 2.3.2 Study Day

Study Day will be calculated relative to the day of first dose (defined as Day 1).

If the assessment (or event) date falls on or after the date of first dose then

$$\text{Study Day} = \text{Assessment Date} - \text{Date of First Dose} + 1$$

If assessment date falls before the date of first dose then

$$\text{Study Day} = \text{Assessment Date} - \text{Date of First Dose}$$

In the case of adverse events or concomitant medications where the assessment date is partially or completely missing, Study Day and any corresponding durations will follow the conventions given in Section 2.3.4.

### 2.3.3 Time Windows for Analysis

Assessment windows will not be defined for the purpose of classifying measurements obtained outside scheduled assessment times for safety and efficacy analyses. The summary by visit will be based on the observations at scheduled visits only. Shift tables will be based on the observations at all visits including both scheduled and unscheduled visits.

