#### 6.4 Central Laboratory Assessments

Serum samples for laboratory analyses must be obtained at all appropriate visits and will be analyzed by the central laboratory. All serum laboratory testing will be provided to the physician for review and assessment. If the Investigator wishes to obtain a follow-up of an abnormal Day 35 laboratory, this laboratory may be obtained after notification of the Sponsor. The laboratory assessments will be determined as listed in Section 3.4.

Hematology:	Hgb, Hct, RBC, WBC, MCV, MCH, MCHC, RDW, platelets, differential count, reticulocyte count, and reticulocyte hemoglobin content (CHr)
Chemistry:	Sodium, potassium, chloride, BUN, creatinine, albumin, alkaline phosphatase, total bilirubin, GGT, AST, ALT, LDH, calcium, phosphorus, glucose, bicarbonate, and magnesium
Iron indices:	Serum iron, serum ferritin, and total iron binding capacity (TIBC), and percentage serum transferrin saturation (TSAT)
Other:	Serum pregnancy test

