### 7.0 ASSESSMENT OF SAFETY

#### 7.1 Adverse Events

Any untoward medical event experienced by a participant during the course of this clinical trial, whether or not it is related to the investigational product, at any dose, is considered an adverse event (AE).

For any laboratory abnormality, the investigator will make a judgment as to its clinical significance. If the laboratory value is outside the normal limits and is felt to represent a clinically significant worsening from the baseline value, it should be considered an adverse event and should be recorded on the Adverse Events page of the eCRF. If the laboratory value is outside the normal range, but not an adverse event, the investigator should comment on the findings (i.e., “not clinically significant” or “unchanged from baseline”) in the source documentation [laboratory report]. All laboratory values at the end of study/Day 35 that have been deemed clinical significant by the Investigator should be followed until they are back into normal range.

For the purposes of this study, non-serious anemia (Hgb or Hct below the normal range or worsened from baseline) or iron deficiency (iron indices below the normal range or worsened from baseline) will not be considered adverse events. Anemia or iron deficiency will be considered end points if an intervention is required.

To quantify the severity of adverse events, the National Cancer Institute (NCI)-Common Terminology Criteria for Adverse Events (CTCAE), Version 5 or higher should be used to grade all events. These criteria are provided in the procedure manual.

If a CTCAE criterion does not exist, the investigator should use Table 7.1.1 to assign the adverse event grade.

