## 8.0 STATISTICS

All hypothesis tests and confidence intervals will be two-sided. No correction for multiple testing will be applied amongst the secondary endpoints. Except where otherwise noted, the statistical model on which inference is based will include terms for randomization strata.

Continuous variables will be summarized in terms of the number of observations, mean, standard deviation, median, Q1, Q3, minimum and maximum. Other descriptive statistics (e.g., coefficient of variation) may be reported when appropriate. Categorical variables will be summarized using frequency counts and percentages.

Generally, data will be summarized by nominal visit. However, data from both unscheduled and scheduled will be used for determination of last observed value, and in worst- or best-case changes and/or shifts from baseline. Assessment windows will not be defined for the purpose of classifying measurements obtained outside scheduled assessment times.

A complete description of the statistical analyses and methods will be available in a Statistical Analysis Plan (SAP), which will be finalized before the database is locked.

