### **7.3 CLINICAL LABORATORY PARAMETERS**

Laboratory assessments include hematology, clinical chemistry, and iron indices:

- Hematology: Hgb, Hct, RBC, WBC, MCV, MCH, MCHC, RDW, platelets, differential count, reticulocyte count and reticulocyte hemoglobin content (CHr)
- Clinical chemistry: sodium, potassium, chloride, BUN, creatinine, albumin, alkaline phosphatase, total bilirubin, GGT, AST, ALT, LDH, calcium, phosphorus, glucose, bicarbonate and magnesium.
- Iron indices: serum iron, serum ferritin, and total iron binding capacity (TIBC), and percentage serum transferrin saturation (TSAT).
- Other: Serum pregnancy test

All laboratory parameters will be presented in conventional units. The actual value and mean change from baseline to each scheduled visit will be summarized using descriptive statistics by treatment for each laboratory test group above. All abnormal laboratory values will be presented in listings.

Time course table for serum phosphate will be constructed for FCM subjects in safety population. Descriptive statistics of days to first value of specified CTC grade and days to return to normal will be summarized. Only the subjects that were under FCM treatment and had a normal serum phosphate baseline value will be included in this table.

The number and percent of subjects with treatment-emergent potentially clinically significant (PCS) laboratory values after baseline will be summarized by visit and by treatment. The denominator is all subjects with normal baseline and at least one post baseline assessment in the

safety population and the numerator is the number of subjects with PCS (i.e., meets Grade 3 or Grade 4 AE scale defined in Division of AIDS (DAIDS) Table for Grading the Severity of Adult and Pediatric Adverse Events, Version 2.1 from March 2017 (Division of AIDS, National Institute of Allergy and Infectious Diseases, National Institutes of Health, US Department of Health and Human Services)) at any post-baseline visit.

Shift from baseline AE grade to maximum post-baseline AE grade, and shift from baseline to the last visit in terms of AE grade will be summarized by treatment, separately.

The AE grade for Chemistries and Hematology are defined in Appendix 1.1. BUN, hematocrit, bands and iron indices do not have adverse event scales available and are not evaluated separately as possible AEs.

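### The baseline-to-last-visit laboratory shift table has no Day 35 cut-off, so a follow-up sample taken until the value is normal can replace the end-of-study grade

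*SAP*

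**What the plan says.** SAP 7.3 plans two shift tables for laboratory grades. One runs from baseline to the worst post-baseline grade. For the other, the "shift from baseline to the last visit in terms of AE grade will be summarized by treatment". Neither document defines the last visit.

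SAP 2.3.3 says which data feed these tables: "Shift tables will be based on the observations at all visits including both scheduled and unscheduled visits". The same section restricts by-visit summaries to scheduled visits, so the shift tables are treated differently on purpose. Protocol 8.0 agrees with the SAP: "data from both unscheduled and scheduled will be used for determination of last observed value, and in worst- or best-case changes and/or shifts from baseline".

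Two other protocol rules govern samples after Day 35. Section 7.1 says that Day 35 laboratory values "deemed clinical significant by the Investigator should be followed until they are back into normal range". Section 6.4 adds: "If the Investigator wishes to obtain a follow-up of an abnormal Day 35 laboratory, this laboratory may be obtained after notification of the Sponsor". Under section 6.3.4 a participant has completed the study once the Day 35 visit is done, so no scheduled visit exists for a later sample.

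**The concern.** Each rule is reasonable alone. Together they let the value that enters the last-visit table depend on what that value is. A child whose Day 35 result is judged clinically significant is to be resampled, and resampling ends when the result is normal. If those retests count as unscheduled observations, the last one is normal by construction. A child with a graded Day 35 result that the investigator considers unimportant has no required retest, so the Day 35 grade stands.

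The table could then drop abnormalities that an investigator thought worth following and keep those thought trivial. The arms would also be compared at times that differ between children for reasons tied to the outcome. The trigger is investigator judgment in an open-label trial (SAP 1.3.3), so the rate of retesting need not be the same in both arms. Safety is part of the primary objective, and this table is meant to show laboratory status at the end of the study by arm.

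**Working it through.** No figure in the plan needs to be reproduced. The check applies the rules to example records and then counts.

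**Inputs from the documents**
- Data for shift tables: all visits, scheduled and unscheduled, with no end date (SAP 2.3.3; protocol 8.0 agrees).
- Table: baseline grade to grade at the last visit, by treatment (SAP 7.3).
- Follow-up: clinically significant Day 35 values until normal (protocol 7.1); a later sample is permitted (protocol 6.4).
- Grades for high ALT (SAP Appendix 1.1): Grade 1 is 1.25 to <2.5 × ULN, Grade 2 is 2.5 to <5.0 × ULN. The ULN for girls is 34 U/L.
- Planned arm size: 36 (protocol synopsis).

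**Two example girls (assumed values), both with normal ALT at baseline**
- Grade 1 runs from 1.25 × 34 = 42.5 to below 2.5 × 34 = 85 U/L. Grade 2 runs from 85 to below 5.0 × 34 = 170 U/L.
- Girl A: Day 35 ALT is 102 U/L (102/34 = 3.0 × ULN, Grade 2) and is judged clinically significant. It is followed, and an unscheduled sample after Day 35 is normal. Her latest observation is normal, so she appears as normal to normal.
- Girl B: Day 35 ALT is 51 U/L (51/34 = 1.5 × ULN, Grade 1) and is judged not significant. No retest is required. She appears as normal to Grade 1.
- On Day 35 the grades were 2 and 1. The last-visit table shows none and 1.

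**Effect on the counts in one arm (assumed: 4 of 36 children with a graded abnormality at Day 35)**

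| Retested to normal and in the data | Last-visit table as written | Table fixed at Day 35 |
|---|---|---|
| None | 4/36 = 11.1% | 4/36 = 11.1% |
| Half | 2/36 = 5.6% | 4/36 = 11.1% |
| All | 0/36 = 0% | 4/36 = 11.1% |

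**Effect on the comparison.** Suppose both arms have 4/36 at Day 35, with all four retested to normal in one arm and two of four in the other. The table shows 0/36 against 2/36, an apparent gap of 5.6 percentage points where Day 35 shows none. This too rests on assumed counts.

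**What the other outputs keep**
- Maximum-grade shift (SAP 7.3): shows that girl A reached Grade 2, but not that she was at Grade 2 on Day 35.
- Potentially clinically significant (PCS) summary (SAP 7.3): covers only Grade 3 or 4 in children with a normal baseline. Girl A is outside it. So is any child with an abnormal baseline for the parameter. That matters for hemoglobin, because entry requires a screening value below 11 g/dL and Appendix 1.1 grades low hemoglobin.
- By-visit summaries: use scheduled visits, but give values and mean changes, not grades.
- Adverse event records and the listing of abnormal values: keep individual cases, but do not tabulate grades at Day 35.

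No other planned grade tabulation of end-of-study status therefore covers Grades 1–2 or children with an abnormal baseline.

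**The case against.** The strongest reply is that using the last observed value is a coherent and openly stated choice: it separates abnormalities that resolved from those that did not. An abnormality that truly persists is still abnormal on retest and keeps a grade. A reader might infer that persisting abnormalities vanish from the table. They do not; only those that resolved after Day 35 show as normal. What the choice cannot do is describe status at a common time, and it resolves cases selectively, because only some children must be retested.

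Second, a reader might infer that this is the only planned display of laboratory grades at the end of the trial. That is not so. SAP 7.3 summarizes Grade 3–4 values by visit in children with a normal baseline, and by-visit summaries use scheduled visits, so a new Grade 3 ALT at Day 35 would appear there. If that summary is instead read through its numerator, which counts any post-baseline visit, the child is still counted, though without the timing. The gap left is Grades 1–2 and children with an abnormal baseline.

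Third, neither document says that samples taken after completion enter the analysis dataset as unscheduled visits, and protocol 6.4 does not call the later sample a visit. The last visit could be read as Day 35 itself. This stands as a limit on the claim: the effect arises only if the retest is in the data. But nothing excludes such samples, and the stated rule takes in unscheduled observations without an end date.

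Fourth, serum phosphate is not affected through this route. It has no grade row in Appendix 1.1 and has its own table of time to a given grade and time to return to normal.

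**Conclusion.** The point holds in a limited form. As written, the plan allows the last-visit grade to be selected by its own outcome, and the direction is towards normal. It can therefore understate abnormalities present at the end of study and compare the arms at unequal, outcome-dependent times.

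This rests on three conditions: the retest is in the analysis data, the Day 35 value was judged clinically significant (or was otherwise resampled), and it later became normal. The documents settle none of these as to frequency, so the size is unknown; in the assumed case it runs from no change to 4/36 falling to 0/36. A reader might infer a complete loss of such abnormalities. The documents do not support that, because follow-up is recommended or optional in its wording, depends on judgment, and need not reach normal.

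The effect is confined to one descriptive table and to the parameters graded in Appendix 1.1. Protocol 8.5.4 plans no formal tests on laboratory data, and the primary analysis and adverse event counts are untouched. Low severity, but worth correcting because it is cheap.

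**What to change.** In SAP 2.3.3 and 7.3:
- Define the last visit for the shift table as the scheduled Day 35 or early-termination assessment or, if that is missing, the last value before it.
- Exclude samples taken after that assessment from this table.
- Keep unscheduled on-study values for the maximum-grade shift.
- List retests after Day 35 separately as resolution data.

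Because protocol 8.0 also uses unscheduled data for last values and shifts, note the change in SAP section 9.

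The cost is about one sentence of SAP wording, an entry in the change list and a date filter in the table program. No new data are needed. The one loss is that later resolution moves from the table to a listing.
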